## 8. DESCRIPTION OF STUDY TREATMENT

### 8.1. Description of TTI-621

A description of TTI-621 Investigational Drug Product is provided in [Table 8](#). TTI-621 is a soluble recombinant fusion protein created by combining the [CCI](#) human SIRPa (the binding domain for CD47) with the Fc region of human IgG1. [CCI](#)

[REDACTED]

[REDACTED]

[REDACTED]

**Table 8. TTI-621 Investigational Drug Product Description**

Dosage Form	CCI
Unit Dose	TTI-621 with a target protein concentration of CCI mg/mL in CCI mM CCI CCI mM CCI and CCI for Injection, pH CCI
Route of Administration	Intravenous
Physical Description	Protein solution
Storage Conditions	Store frozen at CCI °C to CCI °C ( CCI °F to CCI °F) or colder

### 8.2. Description of Doxorubicin

Doxorubicin hydrochloride is an anthracycline topoisomerase II inhibitor. Doxorubicin HCl Injection is supplied in vials containing 10 mg/5 mL, 20 mg/10 mL, 50 mg/25 mL, 150 mg/75 mL, and 200 mg/100 mL doxorubicin HCl as a clear red solution. Doxorubicin hydrochloride for Injection is supplied in vials containing 10 mg, 20 mg, 50 mg, and 150 mg doxorubicin hydrochloride as a red-orange lyophilized powder. Doxorubicin hydrochloride for Injection is reconstituted with 0.9% Sodium Chloride Injection, USP to obtain a final concentration of 2 mg/mL.

Additional details are provided in the Pharmacy Manual. Sites may follow institutional guidelines for selection of product (Doxorubicin HCl Injection or Doxorubicin Hydrochloride for Injection).

### 8.3. Preparation and Administration of Study Treatments

All administration of study treatments should be performed in a setting with emergency medical facilities and staff who are trained to monitor for and respond to medical emergencies.

#### 8.3.1. TTI-621

As described in [Section 5.2.1.2](#), premedication with acetaminophen, anti-histamine, steroid or a subset of these three agents is required for all subjects prior to each infusion of TTI-621. Modification of the specific agent and/or dosages may be made upon discussion with the Sponsor Medical Monitor.

TTI-621 Drug Product will be [CCI](#) and the required dose diluted into [CCI](#) mL [CCI](#)% [CCI](#) for injection USP as further described in the Pharmacy Manual. If not used immediately, the prepared [CCI](#) may be stored as described in the Pharmacy Manual. The assigned dose of TTI-621 will be administered intravenously over 120 minutes, although a reduction in duration of infusion to not

less than 60 minutes is permitted after completion of Cycle 1 at the discretion of the Investigator in the absence of infusion-related reaction. The start of the infusion (Time 0) is defined as after priming, immediately before commencement of the infusion. End of Infusion is defined as the time immediately after flush.

The individual dose is determined based on the subject's current body weight. Body weight can be rounded per institutional procedures when calculating doses. Body weight will be taken on Day 1 of each cycle for purposes of calculating dosage preparation.

Each subject will receive TTI-621 in accordance with the assigned dose until objective assessment of disease progression, unacceptable toxicity or other reason for treatment discontinuation.

In Cycle 1 through Cycle 6, in which TTI-621 is given in combination with doxorubicin, doxorubicin will be administered first. An observation period is not required before initiation of TTI-621 infusion; however, prophylaxis for infusion-related reaction prior to initiation of TTI-621 infusion is required as described in [Section 5.2.1.2](#).

In Cycle 2 through Cycle 6, in the event that doxorubicin dosing is held due to an adverse event from which the investigator believes the patient will recover and continue treatment, TTI-621 treatment will also be held. The day on which doxorubicin is re-initiated will be considered Day 1 of the cycle, and TTI-621 will be administered as planned on the new Day 1 and subsequent Day 8. Initiation of subsequent cycles will be reset according to the new Day 1.

### **8.3.2. Doxorubicin**

Doxorubicin is standard of care in this patient population and sites may use institutionally-accepted methods for preparation of doxorubicin for infusion to the patient. Doxorubicin should be made up to a volume of 100 mL and administered through a free-flowing catheter at 75 mg/m^2 by intravenous infusion in less than 60 minutes. The rate of infusion should be decreased if erythematous streaking along the vein proximal to the site of infusion or facial flushing occur. Doxorubicin is emetogenic and prophylaxis for emesis prior to each infusion of doxorubicin should be given as described in [Section 5.2.1.1](#). Institutional guidelines for effective prophylaxis, including specific agents, additional agents and regimens, are acceptable. Cardioprotective prophylaxis must be implemented no later than initiation of Cycle 5 as described in [Section 5.2.1.1](#). In accordance with NCCN and ASCO guidelines, all patients should receive prophylaxis with G-CSF for prevention of febrile neutropenia. Suggested prophylaxis is pegfilgrastim but other G-CSFs can be considered per the treating physician's discretion; discussion with the Sponsor Medical Monitor is encouraged.

### **8.4. Blinding of Treatment**

This is an open-label study; study treatments will not be blinded.

### **8.5. Treatment Compliance**

The study treatments will be administered by personnel at the study site to ensure compliance.

## 8.6. Study Drug Accountability

Study personnel will maintain accurate records of study treatment shipments, receipts and administration. The site is responsible for the return or destruction of TTI-621 as required.

## 8.7. Concomitant Medications

Patients are allowed to continue medications that they are taking at baseline. Patients may also receive concomitant medications that are medically indicated as standard care for the treatment of symptoms and intercurrent illnesses. Medications to treat concomitant diseases, e.g., diabetes, hypertension, chronic obstructive pulmonary disease, are allowed. Patients will receive prophylaxis medications to prevent development of infusion-related reactions prior to infusions of TTI-621 and may also receive therapy for symptom control and/or to mitigate side effects of the study medication as clinically indicated, as well as best supportive care as per institutional guidelines. This may include, e.g., anti-emetics, anti-diarrheals, anti-cholinergics, anti-spasmodics, anti-pyretics, anti-histamines, analgesics, antibiotics and other medications such as analgesics, electrolyte replacement, hydration, and/or blood product transfusions intended to treat symptoms. Other prescribed medications for non-neoplastic conditions are allowed, as well as vitamins and nutritional supplements (at doses per the Recommended Dietary Allowance or supplementing a known deficiency). The Investigator should instruct the patient not to take any additional medications (including over-the-counter products) during the study without prior consultation.

Patients must not receive live, attenuated vaccines (e.g., FluMist®) within four weeks prior to first day of study treatment, at any time during the study, or through 90 days after the last dose of TTI-621. Inactivated vaccines are allowed. Influenza vaccination should be given during influenza season only (approximately October to March).

Doxorubicin is a major substrate of cytochrome P450 CYP3A4 and CYP2D6, and P-glycoprotein (P-gp). Clinically significant interactions have been reported with inhibitors of CYP3A4, CYP2D6, and/or P-gp (e.g., verapamil), resulting in increased concentration and clinical effect of doxorubicin. Inducers of CYP3A4 (e.g., phenobarbital, phenytoin, St. John's Wort) and P-gp inducers may decrease the concentration of doxorubicin. Concurrent use of inhibitors and inducers of CYP3A4, CYP2D6 or P-gp must be avoided when doxorubicin is being administered.

Due to potential impact on metabolism of both TTI-621 and doxorubicin, THC/CBD and herbal products are prohibited while the patient is receiving treatment on study. The Investigator may discuss specific patients with the Sponsor Medical Monitor.

All concomitant medications, including dose and reason for administration, will be recorded in the eCRF.

### 8.7.1. Concomitant Corticosteroids

Chronic use of steroid above a daily equivalent dose of 20 mg prednisone is not permitted on study.

**8.7.2. Concomitant Hematopoietic Growth Factors and Blood Products**

Myeloid growth factors are permitted for treatment-emergent Grade 3 or Grade 4 neutropenia. Likewise, erythropoiesis-stimulating or megakaryopoiesis-stimulating agents may be used for treatment-emergent anemia or thrombocytopenia, respectively. Transfusion thresholds for blood product support will be in accordance with institutional guidelines.

ASCO guidelines for use of WBC growth factors provide that 'prophylactic use of WBC growth factors for prevention of febrile neutropenia is warranted when the risk of febrile neutropenia is approximately 20% or higher and no other equally effective and safe regimen that does not require CSFs is available. Primary prophylaxis is recommended for the prevention of febrile neutropenia in patients who are at high risk on the basis of age, medical history, disease characteristics, and myelotoxicity of the chemotherapy regimen.' The NCCN guidelines for hematopoietic growth factors classify soft tissue sarcoma treated with doxorubicin as an example of disease setting and chemotherapy regimen with a high risk for febrile neutropenia (>20%) and recommends G-CSF prophylaxis for patients with high risk (>20%) of febrile neutropenia.

Thus, all patients receiving TTI-621 in combination with doxorubicin should receive prophylaxis with G-CSFs for prevention of febrile neutropenia associated with doxorubicin. Suggested prophylaxis is pegfilgrastim and discussion with the Sponsor Medical Monitor regarding the specific agent is encouraged.

**8.7.3. Concomitant Anti-Coagulants**

Use of selected reversible anti-coagulants (low molecular weight heparin, heparin, warfarin or dabigatran) for prevention or treatment of thrombosis is permitted per the 2017 NCCN guidelines, "Cancer-Associated Venous Thromboembolic Disease", with dose adjustments for thrombocytopenia per local institutional guidelines.

## 9. MONITORING AND MANAGEMENT OF EXPECTED OR POTENTIAL ADVERSE EVENTS

Patient safety will be monitored throughout the study. Documented adverse events observed, mentioned or spontaneously reported by the subject will be documented. The Investigator will be responsible for monitoring the safety of patients and for alerting the Sponsor or its designee to any event that seems unusual, even if this event may be considered an unanticipated benefit to the patient. The investigator is responsible for appropriate medical care of patients during the study and for adverse events that are serious in nature, considered related or unrelated to the study intervention, or that caused the patient to discontinue before completing the study. The patient should be followed until such an adverse event is resolved or explained.

All laboratory abnormalities and adverse events will be graded according to NCI CTCAE version 5.0.

In the following section, guidelines are presented for management of adverse events attributed to TTI-621 ([Section 9.2](#)) or doxorubicin ([Section 9.3](#)) and management of adverse events when attribution to neither agent is possible in the opinion of the Investigator ([Section 0](#)).

### 9.1. Prophylaxis for Expected Adverse Events

Prophylaxis for known adverse events associated with doxorubicin or TTI-621 are described in [Section 5.2.1](#). All supportive measures consistent with optimal patient care according to institutional standards should be provided throughout the study. Emergency resuscitation equipment and medications should be readily available. Additional supportive measures should also be available and may include epinephrine, antihistamines, corticosteroids, IV fluids, vasopressors, oxygen, bronchodilators and acetaminophen.

### 9.2. Management of Adverse Events Associated with TTI-621

#### 9.2.1. TTI-621 Treatment Interruptions

Treatment with TTI-621 may be interrupted for up to 42 days for toxicity; treatment may be interrupted for up to 21 days for reasons unrelated to toxicity if the patient is receiving clinical benefit and after discussion with the Sponsor Medical Monitor. Treatment may be re-instated after discussion with the Sponsor Medical Monitor. In general, if an interruption of more than 42 days is required due to adverse events, TTI-621 will be permanently discontinued; however, if in the judgment of the Investigator, the patient is likely to derive clinical benefit from TTI-621 after a hold of more than 42 days, study drug may be re-started with the approval of the Sponsor Medical Monitor. The infusion duration may be increased and the prophylaxis regimen may be altered after discussion with the Sponsor Medical Monitor, but the TTI-621 dose level does not require modification when administration is re-started. Longer interruptions may be acceptable on a patient-by-patient basis at the discretion of the Investigator after discussion with the Sponsor Medical Monitor.

In Cycle 2 through Cycle 6, in the event that doxorubicin dosing is held due to an adverse event from which the investigator believes the patient will recover and continue treatment, TTI-621 treatment will also be held. The day on which doxorubicin is re-initiated will be considered Day 1 of the cycle, and TTI-621 will be administered as planned on the new Day 1 and subsequent Day 8. Initiation of subsequent cycles will be reset according to the new Day 1.

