**Table 1. Adverse Events of Any Grade Assessed as Related to Treatment in  $\geq$  5% of Subjects**

Treatment-Related Adverse Event (Preferred Term)	Number of Subjects (Percent)
Any	193 (82%)
Infusion-Related Reaction	103 (44%)
Chills	49 (21%)
Platelet Count Decreased	37 (16%)
Fatigue	36 (15%)
Thrombocytopenia	34 (14%)
Anemia	30 (13%)
Pyrexia	26 (11%)
Nausea	25 (11%)
Diarrhea	22 (9%)
Headache	18 (8%)
Vomiting	16 (7%)
Hypotension	13 (6%)

A total of 91 subjects (39%) experienced a treatment-related adverse event Grade  $\geq$  3, summarized in [Table 2](#). The most frequently-reported treatment-related Grade  $\geq$  3 adverse events were platelet count decreased (30 subjects, 13%), thrombocytopenia (23 subjects, 10%) and anemia (20 subjects, 9%). The majority of infusion-related reactions observed across the overall study population were Grade 1 or Grade 2, with only 8 patients (3%) experiencing a Grade  $\geq$  3 reaction.

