**9.2.3. TTI-621 Dose Modification Guidelines**

The expansion portion of the study is intended to evaluate two dose levels of TTI-621. The lower dose level will be 0.2 mg/kg but the higher dose level is not yet known. Therefore, [Table 10](#) describes modifications for a range of target starting dose levels (Dose Level 1). Provision is not made for treatment with TTI-621 at a dose level below 0.2 mg/kg, but a lower dose level may be allowed after consultation with the Sponsor Medical Monitor for a patient who is receiving clinical benefit and remaining on treatment is, in the opinion of the Investigator, a reasonable treatment option for the patient.

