**Table 13. Management of Hematologic Adverse Events Associated with TTI-621 Administration**

Note that specific guidelines for management of thrombocytopenia regardless of attribution to TTI-621 and/or doxorubicin are provided in [Table 22](#) and [Table 23](#) and are not described here.

Observation	Management Guidelines
Grade 4 neutropenia lasting > 72 hours	
 
Delay TTI-621 dosing until the re-treatment criterion (ANC <math>> 1.0 \times 10^9/L</math>) is met, then resume TTI-621: 
 
At the same dose if dose delay was <math>\leq 1</math> week
 
One dose level reduction if dose delay was <math>> 1</math> week
 
One dose level reduction if the event recurs
 
 
 

Grade 3 febrile neutropenia lasting > 72 hours Grade 3 neutropenia with clinical evidence of infection Grade 4 febrile neutropenia	
 
Delay TTI-621 dosing until the re-treatment criterion (ANC <math>> 1.0 \times 10^9/L</math>) is met, then resume TTI-621 at one dose level reduction
 

Grade 3 anemia	
 
Delay TTI-621 dosing until resolution to Grade <math>\leq 1</math> or baseline, then resume TTI-621 treatment: 
 
At the same dose if dose delay was <math>\leq 1</math> week
 
One dose level reduction if dose delay was <math>> 1</math> week
 
One dose level reduction if the event recurs
 
 
 

Grade 4 anemia	
 
For Grade 4 events, discontinuation of TTI-621 should be considered. If, per Investigator's assessment, it is in the patient's best interest to continue the treatment, TTI-621 treatment can be resumed when the AE resolves to a level that meets re-treatment criteria
 

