**Table 14. Management of Non-Hematologic Adverse Events Associated with TTI-621 Administration**

Observation	Management Guidelines
Grade $\geq 3$ events with the following exceptions: 
 
• Nausea and/or vomiting lasting <math><72</math> hours with supportive care
 
• Fatigue lasting <math>\leq 72</math> hours
 
• Laboratory abnormalities lasting <math><72</math> hours and judged by the Investigator as not clinically significant
 
	
 
• For Grade 3 events, delay TTI-621 dosing until the re-treatment criteria are met, then resume TTI-621 at one dose level reduction
 
• No dose reduction is required for the exceptions listed
 
• For Grade 4 events, discontinuation of TTI-621 should be considered. If, per Investigator's assessment, it is in the patient's best interest to continue the treatment, TTI-621 treatment can be resumed when the AE resolves to a level that meets re-treatment criteria
 

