**Table 15. Management of other Treatment-Related Adverse Events**

Severity of Event	Management Guidelines
Grade 1	
 
• Maintain TTI-621 dose level
 
• Provide treatment to control symptoms if applicable
 

Grade 2 (tolerable)	
 
• Maintain TTI-621 dose level
 
• Provide treatment to control symptoms if applicable
 

Grade 2 (intolerable)	
 
• Hold administration of TTI-621 until the adverse event recovers to Grade <math>\leq 1</math> or to baseline level, then resume treatment with TTI-621
 

Grade 3	
 
• Hold administration of TTI-621 until the adverse event recovers to Grade <math>\leq 1</math> or to baseline level, then resume treatment with TTI-621
 

Grade 4	
 
• Discontinue TTI-621 unless patient is receiving clinical benefit, adverse event recovers to baseline level and treating physician recommends continuation of treatment at a lower dose level or under a modified schedule
 

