$50 \times 10^9 – 25 \times 10^9/L$	
 
Omit TTI-621 on Day 8
 
Monitor platelet recovery (CBC twice weekly recommended)
 
Consider platelet transfusion per ASCO guidelines if clinically indicated
 
On Day 1 of next cycle: 
 
if platelets have recovered to <math>\geq 75 \times 10^9/L</math>, initiate cycle with doxorubicin at the same dose and TTI-621 at one dose level reduction
 
if platelets have not recovered to <math>\geq 75 \times 10^9/L</math>, hold doxorubicin and TTI-621 and monitor platelets; initiate the cycle when platelets recover to <math>\geq 75 \times 10^9/L</math> with doxorubicin at same dose and TTI-621 at one dose level reduction
 
 
 
In the case of a second occurrence of platelet count decrease to <math><50 \times 10^9</math>, follow the guidelines above or consult with the Sponsor Medical Monitor regarding management
 
The reduced dose of TTI-621 should be used for the remaining combination cycles
 
When the subject completes the combination portion of the study and moves to TTI-621 monotherapy: 
 
the original TTI-621 dose level should be re-instated and platelet counts monitored
 
in the case of platelets <math>< 50 \times 10^9/L</math> without other causality on Day 15, hold TTI-621 until platelets are <math>\geq 50 \times 10^9/L</math> and then continue with TTI-621 at a one dose level reduction
 
on second occurrence of platelets <math>< 50 \times 10^9/L</math> without other causality, reduce TTI-621 by an additional dose level and monitor for tolerability or consult with the sponsor medical monitor regarding management
 
in the absence of disease progression, further dose reductions may be implemented after discussion with the sponsor medical monitor
 
 
 

Platelet Count on Day 8	Management Guidelines

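### Section 9.2.1 says without limit that the TTI-621 dose need not change on restart, which contradicts the one-level reductions that Tables 13, 14 and 21–23 require after defined toxicities

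*Protocol*

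**What the plan says.** Protocol Section 9.2.1 lets TTI-621 be held for up to 42 days for toxicity, or up to 21 days for other reasons, and for longer with Medical Monitor approval. It then says that infusion time and prophylaxis may be changed, but that "the TTI-621 dose level does not require modification when administration is re-started".

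The event-specific tables in Section 9 set their own restart doses:

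- Table 13 (hematologic events related to TTI-621), for Grade 4 neutropenia lasting over 72 hours and for Grade 3 anemia: "One dose level reduction if dose delay was" longer than one week. The same applies if the event recurs. The row for febrile neutropenia and neutropenia with infection requires a reduction whatever the delay.
- Table 14 (Grade 3 non-hematologic events outside its listed exceptions): "delay TTI-621 dosing until the re-treatment criteria are met, then resume TTI-621 at one dose level reduction".
- Table 21 (events of Grade 3 or higher that cannot be attributed to one drug): both drugs go down one level at the first appearance and one more at the first re-appearance.
- Table 22 (combination cycles), for Day 8 platelets of 25–50 x 10^9/L: the next cycle starts "with doxorubicin at same dose and TTI-621 at one dose level reduction". Platelets below 25, or clinically relevant bleeding, lower both drugs. Table 23 gives a similar rule for TTI-621 in monotherapy.

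Section 9.2.2 says that dose modifications for specific events are found in Tables 12–15 and 21–23. Table 10 defines the levels. Its step below 0.2 mg/kg is to discontinue, and Section 9.2.3 adds: "Provision is not made for treatment with TTI-621 at a dose level below 0.2 mg/kg". An exception is possible after Medical Monitor consultation for a patient who is benefiting.

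**The concern.** Section 9.2.1 and the tables answer the same question, namely what dose to give when dosing resumes after a toxicity hold, and they answer it differently. Section 9.2.1 comes first and is worded as a general rule.

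The stake is safety and consistency of dosing. A patient could go back to full dose after an event for which the tables call for less drug. Two sites could also handle the same event differently. Treatment delays and discontinuations are named in the safety endpoints, so an avoidable difference between sites in restart dose adds noise to data the trial means to report.

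**Working it through.** No sample size, power or error rate is involved, so the check sets the texts side by side.

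**Step 1. Restart dose by event.** Under 9.2.1 the entry would be *same dose* in every row.

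| Source | Event behind the hold | Restart dose in the table | Agrees with 9.2.1? |
|---|---|---|---|
| Table 12 | Grade 3 infusion-related reaction | No reduction needed | Yes |
| Table 13 | Grade 4 neutropenia >72 h or Grade 3 anemia; delay of one week or less, no recurrence | Same dose | Yes |
| Table 13 | Same events; delay over one week, or recurrence | One level down | No |
| Table 13 | Febrile neutropenia / neutropenia with infection row | One level down | No |
| Table 14 | Grade 3 non-hematologic, outside the exceptions | One level down | No |
| Table 21 | Unattributable Grade 3 or higher, within its scope | One level down, both drugs | No |
| Table 22 | Day 8 platelets <50 x 10^9/L, or clinically relevant bleeding | TTI-621 one level down | No |
| Table 23 | Day 15 platelets <50 x 10^9/L, or bleeding attributed to study drug | One level down | No |

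The conflict is confined to defined events. It is not present for every hold.

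**Step 2. What one level means (Table 10).**

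- From 2.0 mg/kg: 1.4 mg/kg, a cut of (2.0 − 1.4)/2.0 = 30%.
- From 1.0 mg/kg: 0.7 mg/kg, a cut of (1.0 − 0.7)/1.0 = 30%.
- From 0.7 mg/kg: 0.5 mg/kg, a cut of (0.7 − 0.5)/0.7 = 29%.
- From 0.2 mg/kg: discontinue, unless the Section 9.2.3 exception is granted.

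**Step 3. Can a narrower reading of 9.2.1 remove the conflict?**

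- *It covers only holds over 42 days, the case in the sentence before it.* No words say so, and the conflict would remain. Table 13 requires a reduction once the delay passes 7 days, and 43 > 7. Table 14 has no upper limit on the delay.
- *It means only that an interruption does not in itself call for a lower dose.* This would fit Tables 14 and 21–23, where the event is the trigger. It fails for two Table 13 events, because there the length of the delay is itself a trigger.
- *It is permissive, since it forbids nothing.* It does not forbid a reduction. But saying that none is required is the opposite of a table that requires one.
- *Section 9.2.2 hands the question to the tables.* This is the most natural reading, but 9.2.2 states no order of precedence.

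**The case against.** The strongest reply is that nobody reading the whole chapter would be misled. Section 9.2.2 follows directly and sends the reader to the tables for event-specific dosing. Section 9.2.3 carries the heading on dose modification. The disputed sentence opens with infusion time and prophylaxis and matches Table 12 on infusion reactions. Section 9.2.1 also calls for discussion with the Medical Monitor before treatment is re-instated, and the regular calls in Section 13.8 give a further check. Most of this stands: the tables are very likely the intended rule, and a wrong restart would often be caught. It does not make the sentence correct. A dosing rule should not depend on a reader inferring which of two opposed instructions wins.

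A reader might go further in three ways that the documents do not support.

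- *That the floor at 0.2 mg/kg makes the low dose look less tolerable, and that the SAP hides this.* The floor is a stated choice with an exception. Table 10, with Section 5.3 listing discontinuation of TTI-621 among its stopping criteria, makes stopping the default. SAP 6.1 gives Cohort A its own group. SAP 7.2 summarizes reasons for stopping each drug, and SAP 9.3 tabulates Grade 3 or higher events, reductions and permanent discontinuations by group. A separate count of stops due only to the floor would need a subjective attribution and is a matter of preference.
- *That the rates in study TTI-621-01 give a number of affected patients.* The 22% with Grade 3 or higher thrombocytopenia does not convert to Day 8 counts below 50 x 10^9/L. Protocol 3.7.1 says the falls resolved by the next weekly infusion, and 3.8.1 says most counts were back to baseline within a week. No rate is given for 0.2 mg/kg with doxorubicin.
- *That the primary efficacy result is affected.* Nothing in the documents links this sentence to the response rate or to the Simon rule.

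**Conclusion.** The point holds in a limited form. The restart sentence in Section 9.2.1 is wrong as written: it is unqualified, and it contradicts Tables 13, 14 and 21–23 for the events listed above. It does not contradict Table 12, or the Table 13 rows that allow the same dose after a delay of one week or less.

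The fault is minor. For an affected patient on 0.7, 1.0 or 2.0 mg/kg the two instructions differ by about 30% of the dose. On 0.2 mg/kg they differ between continuing and stopping, subject to the Medical Monitor exception. How many patients this touches cannot be stated from the documents. The conclusion rests on the words alone and assumes that the tables are the rule the sponsor wants, as Section 9.2.2 suggests.

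**What to change.** End the Section 9.2.1 sentence with: *unless Tables 13, 14 or 21–23 require a dose reduction, in which case the table applies*. Table 10 and Section 9.2.3 then settle what happens at 0.2 mg/kg without further wording.

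The cost is one protocol clarification letter. SAP 4.3.2 shows that a study change has already been issued through PACL No 5, which I read as a letter of this kind. No visit, test, analysis or SAP table changes. The benefit is limited to patients still being dosed when the letter goes out.
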